10.3. Amendments

We will notify the METC UMCG and competent authority about substantial amendments. We will inform the sponsor to record and file non-substantial amendments and we will inform the METC UMCG and competent authority.

10.4. Annual progress report

The project leader will submit a summary of the progress of the trial to the METC UMCG once a year, with information on the date of inclusion of the first subject, numbers of subjects included and numbers of subjects that have completed the study, serious adverse events, other problems, and amendments. It is to be expected to finish the study within two years of time. The final report will be submitted accordingly.

10.5. Temporary halt and (prematurely) end of study report

The sponsor will notify the METC UMCG and the competent authority of the end of the study within a period of 90 days. The end of the study is defined as completion of study procedures in the last patient. The sponsor will notify the METC UMCG immediately of a temporary halt of the study, including the reason of such an action. In case the study is ended prematurely, the sponsor will notify the METC UMCG and the competent authority within 15 days, including the reasons for the premature termination. Within one year after

Version number: 4 29 of 41

the end of the study, the investigator will submit a final study report with the results of the study, including any publications/abstracts of the study, to the METC UMCG and the Competent Authority.

10.6. Public disclosure and publication policy

We will write a manuscript about the results of this study, which we will submit to a peerreviewed scientific medical journal. After publication we will make the dataset publicly available on request. This raw data should be made available for future research, unrelated to patient identity.

Version number: 4

11. STRUCTURED RISK ANALYSIS

11.1. Potential issues of concern

a. Level of knowledge about mechanism of action

Previous studies have investigated the risk of training in AAA patients (8, 9, 27, 28) and in patients with a thoracic aorta aneurysm (TAA)(29). These studies do not report mortality due to training or exercise. Thanks to the change in preoperative management, patients are offered home monitoring to intensify daily communication with the hospital, and to enhance safety.

b. Previous exposure of human beings with the test product(s) and/or products with a similar biological mechanism

Human beings with an AAA have been exposed to exercise previously.

c. Can the primary or secondary mechanism be induced in animals and/or in *ex-vivo* human cell material?

Not applicable

d. Selectivity of the mechanism to target tissue in animals and/or human beings

Not applicable

e. Analysis of potential effect

The potential effect of exercise is improvement of condition. A side effect might be elevation of blood pressure, but it is expected to contain the aneurysm, as no side effect have been mentioned previously (see section 10.1a as well).

f. Pharmacokinetic considerations

Not applicable

Version number: 4 31 of 41

g. Study population

Patients with an indication for AAA repair, endovascular or open. Standard care is performed. Subjects are asked to improve their condition with exercise training.

h. Interaction with other products

Not applicable

i. Predictability of effect

Not applicable

j. Can effects be managed?

Due to home monitoring and weekly follow up by the physical therapist, effects of the training are followed closely. In case of deterioration, treating physician will be contacted. Either through the Luscii app, by email or by telephone.

11.2. Synthesis

The risks of this study are very low. To reduce the risk, patients will be monitored during their study activities.

32 of 41

Version number: 4

Appendix 1; Exercise scheme for monitoring at home

	Datum	Tijd	Zuurstof	Bloed	Tijd	Zuurstof	Bloed	Verzonden
		start	saturatie	druk	einde	saturatie	druk	naar de
		training			training			Luscii app?
Ма					_			Ja / Nee
Di								Ja / Nee
Woe	Fysio							Ja / Nee
Don								Ja / Nee
Vrij								Ja / Nee
Ма								Ja / Nee
Di								Ja / Nee
Woe	Fysio							Ja / Nee
Don								Ja / Nee
Vrij								Ja / Nee
Ма								Ja / Nee
Di								Ja / Nee
Woe	Fysio							Ja / Nee
Don								Ja / Nee
Vrij								Ja / Nee
Ма								Ja / Nee
Di								Ja / Nee
Woe	Fysio							Ja / Nee
Don								Ja / Nee
Vrij								Ja / Nee
Ма								Ja / Nee
Di								Ja / Nee
Woe	Fysio							Ja / Nee
Don								Ja / Nee
Vrij								Ja / Nee
Ма								Ja / Nee
Di								Ja / Nee
Woe	Fysio							Ja / Nee
Don								Ja / Nee
Vrij								Ja / Nee
Ма								Ja / Nee
Di								Ja / Nee
Woe	Fysio							Ja / Nee
Don								Ja / Nee
Vrij								Ja / Nee

Appendix 2; Exercise scheme at home and with the physical therapist

Maandag	Dinsdag	Woensdag	Donderdag	Vrijdag
20 minuten	20 minuten	Fysiotherapeut	20 minuten	20 minuten
wandelen	fietsen		wandelen	fietsen
2 minuten	2 minuten	Steep ramp test	2 minuten	2 minuten
traplopen	traplopen		traplopen	traplopen
1 minuut	1 minuut	HIIT	1 minuut	1 minuut
opstaan-zitten-	opstaan-zitten-		opstaan-zitten-	opstaan-zitten-
opstaan	opstaan		opstaan	opstaan

Table: example of a weekly training program

Thuis (4x per week): vaste tijd (bvb. 9u – 10u) overeengekomen met de fysiotherapeut.
Van tevoren zuurstofsaturatie, pols, RR en aantal sigaretten via de Luscii app
Op basis van CPET:

- 10 / 20 / 30 minuten per dag matig-intensief actief zijn (thuis, mensen merken dat ze meer moet ademhalen):
 - Wandelen
 - o Fietsen
- 1 / 2 / 5 minuten hoog-intensief (thuis):
 - Traplopen
 - o Opstaan uit de stoel en weer gaan zitten.

Na de training wederom O2, pols, RR via de Luscii app doorsturen.

Één keer per week fysiotherapie

[figure not shown]
Van tevoren zuurstofsaturatie, pols, RR en aantal sigaretten via de Luscii app Op basis van aangepaste steep ramp test (10 W /10 s):

Nadat de aangepaste SRT op baseline is uitgevoerd (Figuur 1, Grafieken A en C), kan het (gedeeltelijk) gesuperviseerde trainingsprogramma, bestaande uit 3 HIIT-sessies van 25 minuten per week, worden uitgevoerd in de leefomgeving van de patiënt (in de eerste lijn of thuis).

- Elke trainingssessie bestaat uit een warming-up van 3 minuten op een belasting van 20 W, gevolgd door 14 arbeidsintervallen van 30 seconden op een hoge intensiteit van 60% van de SRT Wpiek
- Afgewisseld met 14 herstelintervallen van 60 sec op een lage intensiteit van 20 W

 Waarna een cooling-down van 1 minuut volgt op een belasting van 20 W (Figuur 1, grafieken B en C).

De trainingsintensiteit tijdens de arbeidsintervallen met hoge intensiteit komt overeen met ongeveer 90% van de CPET Wpiek. De aangepaste SRT dient wekelijks of tweewekelijks herhaalt te worden om veranderingen in de cardiorespiratoire fitheid te monitoren, terwijl het programma dienovereenkomstig kan worden aangepast om een adequate trainingsprikkel te behouden.

Appendix 3; Automatized answers Luscii.

Pulsoximeter		
Eerste meting (voor de training)	Zuurstofsaturatie 95 of lager	even rustig zitten, haal een paar keer diep adem en meet je zuurstofgehalte over een kwartier nog een keer. Je vindt de meting Zuurstofgehalte voor de training bij Zelfzorg onder het kopje Metingen. Zorg ervoor dat je handen warm zijn en haal eventuele nagellak of gelnagels weg. Blijft je zuurstofgehalte lager dan 95%? Overleg dan met je fysiotherapeut of je mag gaan trainen.
Eerste meting (voor de training)	Zuurstofsaturatie 95,1 of hoger	Je zuurstofgehalte is goed, je kan starten met je training. Vergeet niet om na de training je metingen in te vullen!
Tweede meting (na de training)	Zuurstofsaturatie 90 of lager	Je zuurstofgehalte is aan de lage kant. Train morgen iets minder hard en bespreek dit advies met je fysiotherapeut.
Tweede meting (na de training)	Zuurstofsaturatie 90 of hoger	Goed gewerkt, volgende keer weer een stukje beter. Gefeliciteerd!
Pols		
Eerste meting (voor de training)	Hartslag 70 of lager	Je hartslag is wat laag. Doe een lichte warming-up en bespreek dit advies met je fysiotherapeut. Meet na de warming-up nog een keer je hartslag. Je vindt de meting Hartslag voor de training bij Zelfzorg onder het kopje Metingen. Blijft je hartslag lager dan 70? Overleg dan met je fysiotherapeut of je door mag gaan met trainen.
Eerste meting (voor de training)	Hartslag 120 of hoger	Je hartslag is wat snel. Ga even rustig zitten en meet je hartslag over een kwartier nog een keer. Bespreek deze meting met de fysiotherapeut.
Tweede meting (na de training)	Hartslag 100 of hoger	Je hartslag is op dit moment wat hoog. Train morgen iets minder hard en bespreek dit advies met je fysiotherapeut.
Derde meting (30 seconden na de training)	Hartslag 120 of hoger	Kan een foute meting zijn. Als het morgen weer zo is, even met de fysiotherapeut bespreken, alstublieft.
Bloeddruk		
Eerste meting (voor de training)	Bovendruk 200mmHg of hoger	Ga niet trainen, meld deze meting volgende keer bij de fysiotherapeut
Eerste meting (voor de training)	Bovendruk onder de 200mmHg	U kan starten met trainen.
Tweede meting (na de training)	Bovendruk 200mmHg of hoger	Stop met trainen, meld deze meting volgende keer bij de fysiotherapeut
Tweede meting (na de training)	Bovendruk onder de 200mmHg	Goed gewerkt, volgende keer weer een stukje beter. Gefeliciteerd!
Stappenteller	 	1
Aantal stappen 5.000-7.500		Je hebt goed getraind vandaag! Probeer dit vol te houden tot aan de operatie.
Te weinig stappen gezet (minder dan 5.000)		Probeer morgen iets meer te trainen zodat je conditie beter wordt voor de operatie. Een betere conditie zorgt voor minder complicaties en een sneller herstel.
Voldoende stappen gezet (meer dan 7.500)		Je hebt goed getraind vandaag! Probeer dit vol te houden tot aan de operatie.

Veel stappen gezet (meer dan 10.000)	Je doet het geweldig en traint fantastisch! Dit zorgt voor een goede conditie en dus een sneller herstel na de operatie!
Roken	
Roken 1-5 sigaretten	Je bent er bijna, stoppen met roken is een kwestie van geduld en doorzettingsvermogen. Nog even doorzetten!
Roken 6-20 sigaretten	Je rookt niet veel, maar elke sigaret minder verkleint het risico. Probeer elke dag iets minder te roken.
Roken > 20 sigaretten	Het is je nog niet gelukt om te stoppen met roken. Minder sigaretten per dag helpt ook! Elke sigaret die je minder rookt zorgt voor een kleiner risico. Probeer dus elke dag iets minder te roken. Je kan het!
Patiënt rookt niet (0 sigaretten per dag.	Je hebt aangegeven niet (meer) te roken, heel goed! Dit zorgt voor een kleiner risico op complicaties en een sneller herstel na de operatie.

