Following the explanation, patients have their intake with a physical therapist. The patients able to perform training, will be prescribed a personalized exercise program and will be followed by a local physical therapist. This includes a training scheme for exercises at home (Appendix 2). They will be asked to train at home and once a week at the physical therapist, check their vital sings with the pulse oximeter and de SMM, and communicate these vital

Version number: 4

signs with the Luscii app to a call center Altide. In case of previously set limitations, this call center will contact the hospital (Appendix 3).

Home-monitored training

All eligible patients will participate in a three-to-nine-week (average of six weeks), partly supervised, home-monitored training program prior to elective AAA-repair. The second CPET measurement is planned after the training program. Training frequency during the prehabilitation will be five sessions per week including a weekly evaluation by the physical therapist. Training sessions at home are prepared and should be able to be performed without extra adjuncts (see below). Before and after home-monitored training sessions without a physical therapist, subjects communicate oxygen saturation, heartrate, blood pressure, number of steps (nS), and number of smoked cigarettes through the Luscii app. According to these measurements, automatic advises will be given through the app (Appendix 3).

To evaluate a difference after the average of six weeks, subjects visit the specialist in sports medicine a second time to perform a CPET. Depending on the performance of patients in relation to the improvement in this second CPET, a subdivision of an improved and a stable (not improved) group will be made. It is expected that improved patients will show an increase of their VO2 at VAT of 1,5 ml/kg/min or more.

Three months after surgery, monitoring is complete, and preoperative patient characteristics of the groups will be compared.

Home-monitored exercises

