6.3. Study procedures

Patients with an indication for AAA repair are routinely prepared for this operation with a visit at the anesthesiologist and the cardiologist. After the indication is set, the minimal waiting time for the operation is usually six weeks on average. This gives the

Version number: 4 21 of 41

subject the opportunity to start training. Surgery will not be postponed for this pilot study.

After the indication and informed consent, a questionnaire will be completed with the help of a professional research-nurse, and a cardiologic consultation will be performed. When subjects are fit for training, they will be informed about the use of the home-monitoring device. This will be followed by a visit at physical therapist (Figure 1).

Estimation of costs Aneurysm in motion					
	WZA (40	patients)	Treant (60 p	Totals	
Intake Luscii	€ 32	€ 1.280	€ 32	€ 1.920	€ 3.200
Alert Luscii	€ 14,70	€ 588	€ 14,70	€ 882	€ 1.470
Costs research bureau (30 minutes)	€ 20	€ 800	€ 20	€ 1.200	€ 2.000
	Totaal 1 jaar	€ 2.668		€ 4.002	
Both hospitals					€ 6.670

Table 2: Expected costs in participating hospitals, without insurance costs.

Following these three explanations (home monitoring, questionnaires, and training), the subject will be asked to start their home training during office hours, following a communication with the communication center of the home monitoring (Luscii). After each training and cooling down, parameters should be imported from the homemonitoring device and feedback will be given from the communication center. In case of anomalous measurements, the hospital will be contacted.

	Action	Conditions	Requirement Fit patients	Requirement Unfit patients
Inclusion criteria	Indication AAA repair	Elective repair	Eligible for inclusion	Eligible for inclusion
Inc	Informed consent	Signed	Eligible for inclusion	Eligible for inclusion
	Questionnaire	Various characteristics	One hour	One hour
	Specialist sports medicine	Consultation and CPET	One hour	-
	Cardiologist	Safe to perform training	Questionnaire and CPET	-
		Unsafe	-	Follow up
ıction	Explanation	Home monitoring device	One hour	-
Introduction	First visit physical therapist	At location physical therapist	One hour	-
iks	Daily training at home	Four days a week	Four hours	-
3-9 weeks	Weekly visit physical therapist	Once a week	One hour	-
Postop	Three months after the operation	Outpatient clinic	Ten minutes	Follow up

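### Appendix 3: a pre-training oxygen saturation that stays at exactly 95 leads neither to the go-ahead nor to the consult instruction

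*Protocol*

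**What the plan says.** The pulse-oximeter block of Protocol Appendix 3 gives these rules for the measurement before training:

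- **Rest and repeat:** "Zuurstofsaturatie 95 of lager". The patient sits quietly, breathes deeply and measures again after a quarter of an hour.
- **Where the repeat is entered:** "Je vindt de meting Zuurstofgehalte voor de training bij Zelfzorg onder het kopje Metingen", the pre-training saturation item.
- **Consult:** "Blijft je zuurstofgehalte lager dan 95%? Overleg dan met je fysiotherapeut of je mag gaan trainen".
- **Go-ahead:** "Zuurstofsaturatie 95,1 of hoger". The message says that the saturation is good and training can start.

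Protocol section 1 (Home-monitored training) makes these messages part of the procedure. After listing the values that patients report around home sessions held without a physical therapist, it says "According to these measurements, automatic advises will be given through the app (Appendix 3").

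**The concern.** The trigger includes 95, the consult condition excludes it, and so does the go-ahead. A patient whose saturation stays at 95 is told that the value is too low to start and is asked to measure again. After that, no stated outcome applies.

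This row serves as a safety check before unsupervised exercise, so each reading should end either in permission to train or in an instruction to ask someone. At its own threshold the rule gives neither. Patients may then act differently on the same reading. One reasons that 95 is not below 95 and trains, which conflicts with the go-ahead limit. Another keeps repeating the measurement or skips the session. Skipped sessions would also bear on adherence, one of the feasibility measures in the Objectives.

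**Working it through.** **Step 1: apply the written rules to a first reading of 95 or lower.**

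| Repeat reading | Rest-and-repeat (≤ 95) | Consult (< 95) | Go-ahead (≥ 95.1) | Decision |
|---|---|---|---|---|
| 94 | yes | yes | no | consult |
| 94.9 | yes | yes | no | consult |
| **95** | **yes** | **no** | **no** | **none** |
| 95.1 | no | no | yes | start |
| 96 | no | no | yes | start |

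The result is the same whether the first reading was 93, 94 or 95. A value strictly between 95 and 95.1 would match no row, but that matters only if the device shows more than one decimal.

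**Step 2: compare with another block of the same appendix.** The blood pressure rows split without a leftover value: no training at 200 mmHg or higher, start at "Bovendruk onder de 200mmHg". The saturation rows do not.

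**Step 3: look for another limit that settles 95.** Section 1 has the call center contact the hospital at preset limits, but it refers back to Appendix 3 and gives no separate saturation figure. Section 6.3 says "In case of anomalous measurements, the hospital will be contacted" and gives no number for anomalous. Neither resolves the value.

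**Step 4: how often could it happen?** The protocol gives no saturation distribution and no display resolution, so every input here is an assumption. Take first and repeat saturations X₁ and X₂ as normal, with mean 95.5 to 97, SD 1.2 to 2 and correlation 0 to 0.8, rounded to a display step d. The case of interest is

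P = P(X₁ < 95 + d/2 and 95 − d/2 ≤ X₂ < 95 + d/2).

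Worked example at the low end (d = 1, mean 97, SD 1.2, correlation 0):

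- P(X₁ < 95.5) = Φ(−1.25) = 0.1056
- P(94.5 ≤ X₂ < 95.5) = Φ(−1.25) − Φ(−2.083) = 0.1056 − 0.0186 = 0.0870
- P = 0.1056 × 0.0870 = 0.0092

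Ranges per pre-training check over all assumed inputs:

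| Display step | Repeat has the same mean | Repeat mean 1 point higher after rest |
|---|---|---|
| 1.0 (whole percent) | 0.9% to 21% | 0.2% to 15% |
| 0.1 (as the limit of 95.1 suggests) | 0.04% to 1.4% | 0.008% to 1.3% |

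Four home sessions a week for 3 to 9 weeks give 4 × 3 = 12 to 4 × 9 = 36 checks. The count per patient then runs from 12 × 0.00008 ≈ 0.001 to 36 × 0.206 ≈ 7.4. The calculation shows only that display resolution matters a great deal: at whole percentages 95 is an ordinary reading, at 0.1 steps a rare one.

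**The case against.** The strongest reply is that this is a copy-edit with little consequence, and much of it stands.

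- **App behavior is inferred.** The row is labelled as the first measurement, and the protocol does not describe how the app handles a repeat. That the patient gets the same message again is likely, not certain. The mismatch between the three limits does not depend on it.
- **The patient does see the consult sentence.** At 95 the message already names the physical therapist as the person to ask if the value stays low, and a sensible patient may call. True, but the condition attached to that advice excludes the patient's reading.
- **Other contacts exist.** Section 6.3 has home training start after a communication with the monitoring center, the therapist reviews findings weekly (section 1), and the call center can alert the hospital. These soften the consequence. None of them states what to do at 95, and a weekly review gives no decision for that day.
- **Part of the message may be lost.** The cell opens in mid-sentence in the available text. The trigger, consult sentence and go-ahead limit are complete, so the comparison holds.
- **It is not the only boundary slip in the appendix.** The heart-rate row pairs a trigger of 70 or lower with a consult below 70, though that message separately tells the patient to discuss the advice with the therapist. After training, a saturation of 90 falls under both the warning and the congratulation. These are separate points that the change proposed here does not repair.

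**Conclusion.** The point holds and is minor. As written, the pre-training saturation rule gives no train-or-consult decision for a repeat of exactly 95, and nothing else in the protocol supplies one. The gap is on the cautious side, since 95 never produces permission to train. The likely cost is a wait, a missed session, or no explicit same-day instruction to consult at that value. The sample size, the responder definition and the primary analysis are not affected.

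The mismatch itself needs no assumption. Its frequency is unknown, and the calculated range should not be quoted as an estimate. That the patient is returned to the same message rests on the inference that a repeat entered under the pre-training item is handled like a first reading.

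**What to change.** In the consult sentence of Appendix 3, replace the condition *lager dan 95%* with *95% of lager*. The consult then has the same limit as the trigger, and every repeat shown in whole percentages or in steps of 0.1 leads either to the consult (95 or lower) or to the go-ahead (95.1 or higher). Moving the trigger to below 95 and the go-ahead to 95 or higher would also close the gap, but it would permit training at a value that the plan now treats as low, so the first option is preferable.

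The cost is one phrase in one automatic app message. It adds no measurement and needs no change to the analysis.

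### Appendix 3 lets one good reading trigger a start message, so a patient with another reading out of limits can be told both to start and to hold off

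*Protocol*

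**What the plan says.** Protocol Appendix 2 has the patient send the readings before training: "Van tevoren zuurstofsaturatie, pols, RR en aantal sigaretten via de Luscii app". Section 1 (Home-monitored training) says the app then gives automatic advice according to Appendix 3, and section 3.1 (Preoperative exercises) also places the three vital-sign measurements before the session.

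Appendix 3 lists the pre-training answers by device:

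- **Saturation 95.1 or higher:** "Je zuurstofgehalte is goed, je kan starten met je training" (oxygen is good, you can start).
- **Saturation 95 or lower:** sit quietly, breathe deeply and remeasure after fifteen minutes. If it stays low, "Overleg dan met je fysiotherapeut of je mag gaan trainen" (ask the physical therapist whether you may train).
- **Pulse 70 or lower:** light warm-up and remeasure, then "Blijft je hartslag lager dan 70? Overleg dan met je fysiotherapeut of je door mag gaan met trainen" (if it stays below 70, ask whether you may continue).
- **Pulse 120 or higher:** "Ga even rustig zitten en meet je hartslag over een kwartier nog een keer" (rest and remeasure after fifteen minutes), then discuss with the physical therapist.
- **Systolic under 200 mmHg:** "U kan starten met trainen" (you can start).
- **Systolic 200 mmHg or higher:** "Ga niet trainen, meld deze meting volgende keer bij de fysiotherapeut" (do not train; report this next time).

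On escalation, section 1 (Recruitment) says "In case of previously set limitations, this call center will contact the hospital (Appendix 3"), and section 6.3 has the hospital contacted about anomalous measurements.

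**The concern.** Two of these answers give permission to train on the strength of a single reading, although three readings are taken to decide whether training is safe. When one reading is acceptable and another is not, the written rules produce two instructions that point in different directions. The protocol does not say which one the patient should follow.

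This matters because section 11.2 names monitoring as the means of reducing risk, and section 3 justifies the close observation by how new training is in AAA patients. Four of the five weekly sessions take place at home (section 1). The clash is sharpest for systolic pressure of 200 mmHg or higher. That is the only outright pre-training ban in Appendix 3, and a normal saturation is enough to contradict it. The ban's own text asks only for a report next time, so it does not direct the patient to anyone before the decision is made.

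**Working it through.** The protocol gives no figure to reproduce here. The check is a count of what the Appendix 3 rules return for each combination of pre-training readings.

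**Inputs (Appendix 3)**

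- Saturation, 2 states: in (95.1 or higher), out (95 or lower).
- Pulse, 3 states: low (70 or lower and still below 70 after the advised warm-up), in range, high (120 or higher).
- Systolic pressure, 2 states: in (under 200), out (200 or higher).

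Combinations: 2 × 3 × 2 = 12. One has everything within limits, so 12 − 1 = 11 have at least one value out.

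**Rule applied.** A start message is issued if saturation is in or systolic is in. A hold answer (do not train, remeasure or consult) is issued if any reading is out. A conflict is both at once.

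| Saturation | Systolic | Start messages | Pulse low | Pulse in range | Pulse high |
|---|---|---|---|---|---|
| in | in | 2 | conflict | all within limits | conflict |
| in | out | 1 | conflict | conflict | conflict |
| out | in | 1 | conflict | conflict | conflict |
| out | out | 0 | hold only | hold only | hold only |

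**Result**

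- Conflicts: 2 + 3 + 3 = 8 of 11. The same figure follows by subtraction: 11 − 3 = 8.
- Exactly one reading abnormal: 4 cases (saturation out, systolic out, pulse low, pulse high). All 4 conflict.
- Pulse left out: 2 × 2 = 4 combinations, 4 − 1 = 3 with a value out, 3 − 1 = 2 conflicts.
- Explicit ban against explicit permission (systolic out, saturation in): 3 of the 11, which is one situation repeated over the three pulse states.

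**Examples**

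- Saturation 97, systolic 210: one start message and one instruction not to train.
- Saturation 93, systolic 140: one start message and one instruction to rest and remeasure.
- Saturation 97, systolic 140, pulse 125: two start messages and one instruction to rest and remeasure.

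**Exposure.** Four home sessions a week (section 1) for 3 to 9 weeks gives 4 × 3 = 12 to 4 × 9 = 36 sessions per patient at which these rules apply.

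**The case against.** The strongest reply is that Appendix 3 is a list of reply texts and not a decision algorithm. The app may combine or suppress answers in ways the protocol does not describe. Section 3.1 requires all three measurements before training starts, which argues against treating one good value as clearance. Section 6.3 says home training starts after a communication with the monitoring center, and the call center contacts the hospital when preset limits are crossed. Training is also confined to office hours (Summary). The hold answer is always sent, and most patients would probably follow it. Finally, only one pre-training answer forbids training. The others ask for a pause, and a patient could remeasure first and start afterwards.

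Parts of this stand. The low-pulse answer is soft, because it allows a warm-up and asks only about continuing. The true permit-versus-forbid clash is confined to high systolic pressure with acceptable saturation. The call center is a real back-stop. The app's actual display logic is not in the document.

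It does not remove the point. The protocol itself writes the answers and says they follow the measurements automatically; any unstated suppression is a guess. The communication mentioned in section 6.3 may be a contact before each session or a single first contact. On either reading, neither it nor the call-center rule withholds a start message or ranks the answers. Low saturation and fast pulse still set wait-and-remeasure against start. The point also survives when pulse is ignored.

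**Conclusion.** The concern holds. As written, Appendix 3 issues contradictory pre-training instructions in 8 of the 11 out-of-limit combinations, in 2 of 3 when pulse is left out, and whenever exactly one reading is abnormal. The most serious case is systolic 200 mmHg or higher with acceptable saturation.

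This rests on reading Appendix 3 as stated, with each answer triggered by its own reading and all triggered answers shown. The counts describe rule combinations, not probabilities: the protocol gives no basis for how often a reading will be out of limits. The safeguard is weakened, not lost, because the hold answer is still sent and the call center remains. The defect concerns operational safety and does not affect the endpoint, sample size or analysis. It should be corrected.

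**What to change.** Amend Appendix 3 and the app configuration as follows:

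1. Issue a single start message only when saturation, pulse and systolic pressure are all within limits, or have been cleared on remeasurement or by the physical therapist.
2. State that any answer to stop, remeasure or consult overrides a start answer.
3. Until the app is changed, reword the two single-reading start answers so that each comments on its own value only, for example that the oxygen level is good, without permission to begin.

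If the app already applies such logic, a sentence in Appendix 3 saying so is enough. The limits themselves remain a matter for the responsible clinicians.

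The cost is an amended appendix and reconfigured messages. The interim step changes two texts. No extra visits, staff or patients are needed.

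### Appendix 3's automatic app answers conflict as written: post-training saturation 90 falls in two rows, and before training permission to start can arrive with an instruction not to train

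*Protocol*

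**What the plan says.** Section 1 (Home-monitored training) has patients send saturation, heart rate and blood pressure through the app before and after each home session, and refers to Appendix 3 for the automatic advice they get back. Appendix 3 is in Dutch and gives one answer per measurement and threshold.

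- **Saturation after training.** The row "Zuurstofsaturatie 90 of lager" tells the patient to ease off tomorrow and talk to the physiotherapist. The row "Zuurstofsaturatie 90 of hoger" congratulates the patient.
- **Saturation before training.** At 95.1 or higher: "Je zuurstofgehalte is goed, je kan starten met je training". At 95 or lower the patient is told to sit, breathe and re-measure after a quarter of an hour, then: "Blijft je zuurstofgehalte lager dan 95%? Overleg dan met je fysiotherapeut of je mag gaan trainen".
- **Systolic pressure before training.** At 200 mmHg or higher: "Ga niet trainen, meld deze meting volgende keer bij de fysiotherapeut". Below 200: "U kan starten met trainen".
- **Pulse before training.** At 120 or higher: "Ga even rustig zitten en meet je hartslag over een kwartier nog een keer". At 70 or lower the patient is told to do a light warm-up, re-measure, and ask the physiotherapist about continuing if the pulse stays low.

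On escalation, Section 1 (Recruitment) says: "In case of previously set limitations, this call center will contact the hospital (Appendix 3". Section 6.3 adds hospital contact for anomalous readings, and Section 11.1(j) adds contact with the treating physician if the patient deteriorates.

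**The concern.** Four home sessions a week are planned (Section 1, Home-monitored exercises), including high-intensity stair-climbing, in patients waiting for aneurysm repair. Section 3.1 lets a home session begin once heart rate, pressure and saturation have been measured, and the app's answers are the immediate response the patient sees.

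Those answers should not say yes and no to the same set of readings. In Appendix 3 they can: one saturation value belongs to two rows, and the pre-training answers are written separately for each measurement with no order of priority. What is at stake is the clarity of a safety instruction to a patient training at home without a therapist present. The endpoint, the training delivered and the analysis are not in question.

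**Working it through.** The plan states no figure to reproduce here. The check applies the thresholds of Appendix 3 as written and lists which answers each reading triggers.

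**1. Saturation after training.** The caution row applies if saturation ≤ 90, the praise row if saturation ≥ 90.

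| Reading | Answers triggered |
|---|---|
| 88, 89 | caution |
| 90 | caution and praise |
| 91, 92 | praise |

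The overlap is confined to the value 90. Other paired rows in the table are cut cleanly: 95 or lower against 95.1 or higher for saturation before training, and 200 or higher against below 200 for pressure. The 90/90 pair therefore departs from the table's own convention.

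**2. Answers before training.** The rows define 2 saturation levels (≤ 95, ≥ 95.1), 3 pulse levels (≤ 70, between 70 and 120, ≥ 120) and 2 pressure levels (< 200, ≥ 200). That gives 2 × 3 × 2 = 12 patterns.

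| Saturation | Systolic | Pulse | Patterns | Answers together |
|---|---|---|---|---|
| ≥ 95.1 | ≥ 200 | any | 3 | *start* and *do not train* |
| ≤ 95 | < 200 | any | 3 | *start* and *sit, re-measure* (saturation) |
| ≥ 95.1 | < 200 | ≥ 120 | 1 | *start* and *sit, re-measure* (pulse) |
| ≥ 95.1 | < 200 | ≤ 70 | 1 | *start* and *warm up, re-measure, consult* |
| ≥ 95.1 | < 200 | between | 1 | *start* only |
| ≤ 95 | ≥ 200 | any | 3 | no *start* answer |

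Sum: 3 + 3 + 1 + 1 + 1 + 3 = 12. Literal start/do-not-train conflicts: 3. Start with sit-and-re-measure: 3 + 1 = 4.

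Examples:
- Saturation 97 with systolic 205 returns *start* and *do not train*.
- Saturation 94 with systolic 150 returns *sit, re-measure* and *start*.
- Pulse 125 with saturation 97 and systolic 150 returns *sit, re-measure* beside two *start* answers.

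**3. Search for a precedence rule.** Section 1, Section 3.1, Section 6.3, Section 11.1(j) and Appendix 3 contain none. Section 1 points to Appendix 3 for the limits at which the call center contacts the hospital, but the appendix marks no such limits. Its warning rows for saturation (2), pulse (4) and pressure (2), 8 in all, each refer to the physiotherapist.

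**The case against.** The strongest reply is that the rows are meant to be read together. Section 3.1 requires all three measurements before a session. The saturation message opens by speaking about oxygen only, while the pressure message is a flat prohibition, so the natural reading is that the prohibition wins. Section 6.3 also places a communication with the monitoring center before the start of training. The table does not describe display order or app logic, so simultaneous display is inferred. At a post-training saturation of 90 the cautious advice still reaches the patient.

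Much of this is fair, and it limits the weight of the point. It does not remove it. The saturation message goes on to permit the session, and the permission in the pressure row, "U kan starten met trainen", does not mention pressure at all. The documents leave the patient to infer that a stop overrides a start. The communication in Section 6.3 may mean no more than sending the readings. The call-center, hospital and physician contacts are real safeguards, but none says which message prevails. Equally, patient-facing messages that do not name the hospital do not prove that the call center works without limits.

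A reader might add the patterns up and call 7 of the 12 contradictory. The documents do not support that. Sitting and re-measuring postpones training and does not forbid it. That total would also leave out the low-pulse row, although that row too makes continuing conditional. Only 3 patterns are literal contradictions.

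**Conclusion.** Appendix 3 is wrong as written in two places: the shared value 90 after training, and the lack of any precedence among the pre-training answers. The second produces 3 of 12 patterns with a literal start/do-not-train conflict, and 4 more in which permission to start accompanies a delay.

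The counts assume that every row is triggered by its own measurement alone, as the table is laid out, and that all three readings are sent for the same session, as Section 1 states. They say nothing about how often the conflicts occur, because the documents give no distribution of readings. After training, the claim is confined to the value 90.

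A reader might infer that patients will train when they should not, or that the trial's results are compromised. The documents support neither: partial safeguards exist, and the primary comparison does not use these messages. The severity is minor.

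**What to change.** 1. Change the post-training praise row to saturation above 90 (90.1 or higher), in line with the 95/95.1 cut used before training.
2. Before training, send permission to start only when saturation is 95.1 or higher, systolic pressure is below 200 and pulse is below 120. Otherwise send only the most cautious answer, with *do not train* overriding all others and *sit, re-measure* next.
3. At pulse 70 or lower, when neither of those answers applies, replace permission to start with that row's own warm-up, re-measure and consult message.

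Applied to the 12 patterns, this gives *do not train* in 6 (all with systolic 200 or higher), *sit, re-measure* in 3 + 1 = 4, the low-pulse message in 1 and *start* in 1, which sums to 12. No pattern then pairs permission to start with another instruction.

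The cost is an amendment of Appendix 3 and a reconfiguration of the app messages. No new measurement or visit is needed.
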